## DOCUMENT HISTORY

Version	Date	Edited by	Comments	Timing in relation to unblinding
1.0	7 June 2020	GM	Approved by signatories, updated to version 1.0	Prior to trial registration
2.0	25 March 2024	GM	Change to inclusion and exclusion criteria, removal of TSC and DMEC, Interim analysis by trial statistician, subgroup analysis, sensitivity analysis, Consort diagram.	After trial registration

## 2. INTRODUCTION

This document details the proposed presentation and analyses for the main analysis reporting results from the USAID and Clearly funded randomised controlled trial PROSPER III (PROductivity Study of Presbyopia Elimination among aRtisans: a randomised trial on the effect of providing near glasses on workplace retention of Indian textile workers). The results reported in this publication will follow the strategy set out here. Subsequent analyses of a more exploratory nature will not be bound by this strategy, although they are expected to follow the broad principles described. The principles are not intended to curtail exploratory analysis (for example, to decide cut- points for categorisation of continuous variables), nor to prohibit accepted practices (for example, data transformation prior to analysis); rather they are intended to establish the rules that will be followed, as closely as possible, when analysing and reporting on the trial and the qualitative sub-study.

The analysis plan will be available on request when the principal manuscripts are submitted for publication. Suggestions for subsequent analyses by journal editors or referees will be considered carefully and carried out, as far as possible, in line with the principles of this analysis plan.

Any deviations from the data analysis plan will be described and the rationale given in the final report of the trial. The analysis will be carried out by an identified, appropriately qualified and experienced statistician, who will ensure the integrity of the data during processing. Examples of such procedures include quality control and evaluation procedures.

## 4. BACKGROUND INFORMATION

### 4.1 Rationale

PROSPER III is a mixed methods randomised controlled trial (RCT) assessing the effect of reading glasses on the retention of presbyopic textile workers in Bangalore, India. PROSPER

III's primary approach is a randomized controlled trial (RCT), and the secondary or embedded approach is a descriptive qualitative study.

#### 4.2 Objectives of the trial

Globally, 3 billion people do not have the eyeglasses they need to earn, learn, travel safely in traffic and participate in civic life. Among these, 1.1 billion people lack a simple pair of reading glasses to correct impaired near vision, called presbyopia. Presbyopia, the essentially universal decline in unaided near vision that occurs with aging, is the world's most common cause of vision impairment. Loss of accommodation (ability to change focus from distance to near) due to presbyopia can begin as early as age 30 years, commonly becomes functionally apparent by 40, and is essentially complete by 55, meaning that presbyopia is most common at the height of the working years. The correction of presbyopia is both safe and affordable: requiring nothing more than a pair of reading glasses to restore vision at near. Despite this, only approximately 10% of people in need of reading glasses in low and middle-income countries actually have them.

Data from the International Labour Organization shows that the rate of having a job among people over the age of 40 in low- and middle-income countries is declining. Our previous randomized trials in India demonstrated that the provision of free reading spectacles significantly improved the productivity of agricultural workers on a tea plantation over the course of a harvest season. The PROSPER trial enrolled 751 adults (mean age 47 years) with uncorrected presbyopia in Assam, India, and showed significantly higher productivity among workers randomized to receive free glasses compared to Controls (21.7% relative productivity increase; effect size 1.01 [95% CI 0.86–1.16];  $p<0.0001$ ). Intervention-group compliance with study glasses reached 84.5% by closeout. Regression model predictors of greater productivity increase included intervention group membership (an extra 5.25 kg of tea leaves picked per day [95% CI 4.60–5.91],  $p<0.0001$ ) and, among intervention participants, older age ( $p=0.039$ ) and better compliance with the intervention ( $p<0.0001$ ). PROSPER I revealed a significant interaction between age and study group for the main study outcome. Older participants in the intervention group had significantly greater productivity increases than younger participants. Older participants in the control group, having more pronounced, uncorrected presbyopia, were less able than their younger peers to take advantage of higher crop yields during the peak high season, resulting in lower productivity increases. This strong interaction of age and productivity with study group adds to the biological plausibility of the results of PROSPER I. To place these results into perspective, the relative productivity increase in the productivity of workers receiving reading glasses was as large as or larger than that reported for any other health intervention trial in low-income and middle-income countries.

In light of the above findings, PROSPER III will assess whether free reading glasses are able to extend the productive working life of workers (i.e increase retention) in textile factories in Bangalore, India. We hypothesise that worker retention over the 18-month evaluation period will be greater in the Intervention compared to the Control group. Additional qualitative data will be collected to enhance understanding of factors affecting retention of study subjects (textile workers aged 30 years and above with uncorrected presbyopia who are employed by Shahi Exports Private Limited in Karnataka, India).

## 4.3 Trial design

PROSPER III is an investigator-masked, multi-centre mixed methods randomized controlled trial.

## 4.4 Eligibility

### 4.4.1 Inclusion criteria

Shahi employees will be eligible to participate if:

- they are aged 30 years or older
- have presbyopia, defined as an unaided near visual acuity of N6.3 or worse in both eyes
- have worked in the production department for 6 weeks or more
- they require a new pair of glasses to improve their near vision
- they have a corrected near visual acuity of N4 or better in both eyes

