## 4.6 Definition of primary and secondary outcomes

### 4.6.1 Primary outcome

The primary objective of the study is to estimate the effect of the provision of free reading glasses on the retention of textile workers employed in Shahi's sewing department. The time-to-event endpoint for PROSPER III is defined as the time between randomization to

Intervention or Control Group and loss of employment at Shahi. Employment status for each participant will be assessed from trial entry to closure as recorded in Shahi's Human Resource Management Database.

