#### 4.6.2 Secondary outcomes

The secondary outcomes are:

- reasons given by supervisor and colleagues of former sew-ers (separately) for workers no longer being employed at Shahi
- proportions of sew-ers who state they are satisfied or very satisfied with work, feel valued or very valued at work, and are likely or very likely to stay with current employer
- change in self-assessed productivity
- self-report of having been approached by their assigned Captain and/or a supervisor
- change in attitude towards eye health, glasses wear and uptake of eyecare services
- changes in skill grade and associated change in wage
- adherence with spectacle wear
- Quality of Life using the THRIVE Near Vision Quality of Life tool.
- intervention cost-effectiveness

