### 5.2.1 Participants randomised in error

- Employees < 35 years, or employed < 6 weeks, or not employed in the sewing department assigned to Intervention Group

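### Eligibility is set for the production department, but the primary objective, two secondary outcomes, the qualitative sub-study and a one-arm randomised-in-error rule refer to sewing, and the SAP never says whether the two are the same workforce

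*SAP*

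**What the plan says.** Section 4.4.1 sets the department criterion: workers must "have worked in the production department for 6 weeks or more". No sewing role is required.

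Section 4.6.1 words the primary objective as the effect on "retention of textile workers employed in Shahi's sewing department". The endpoint that follows is time to loss of employment at Shahi, with no department limit: "Employment status for each participant will be assessed from trial entry to closure".

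Section 4.6.2 lists nine secondary outcomes. Two name sew-ers: "reasons given by supervisor and colleagues of former sew-ers (separately) for workers no longer being employed at Shahi", and the item that begins "proportions of sew-ers who state they are satisfied or very satisfied with work" and goes on to feeling valued and intending to stay. The other seven name no department, for example "changes in skill grade and associated change in wage".

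Section 5.2.1, under minor deviations, lists as randomised in error those younger than 35, those employed for less than 6 weeks, and those "not employed in the sewing department assigned to Intervention Group".

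Section 7.1 analyses all outcomes by intention to treat in everyone allocated. Section 8.1 reports the number randomised in error in the CONSORT flow. Section 10 frames the qualitative hypothesis around sewing operators.

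**The concern.** The terms used for eligibility and for the trial's target population differ, and nothing in the SAP links them. If production is the broader term, a worker can meet every item of section 4.4, be properly randomised, and still be outside the population in the primary objective. The report would then describe a result from production workers as a result for sewing workers.

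The deviation rule adds a second problem. As worded, its department clause reaches only workers assigned to the Intervention Group. The same eligible non-sewing worker is an error in one arm and a valid participant in the other. A reader of the CONSORT diagram would see an apparent imbalance in enrolment errors that comes only from the definition.

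**Working it through.** **1. Does the sample size depend on department?** The inputs in section 4.8 are hazard ratio 0.8, two-sided 5%, 80% power and control retention of 50% at 1 year; section 4.5 gives 1:1 allocation. The Schoenfeld formula, events = 4(z₀.₉₇₅ + z₀.₈₀)² / (ln 0.8)², gives 631 events. Dividing by an event probability of 0.5 gives 631 / 0.5 = 1,262, against the stated 1,260. The figure reproduces, and no department term enters it.

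**2. One worker followed through the plan.** Suppose production includes some non-sewing workers. Take one who is 42, has been in post 6 months, and meets every item of section 4.4.

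| Section | Status of this worker |
|---|---|
| 4.4.1 Inclusion | Eligible |
| 4.6.1 Objective sentence | Outside the named population |
| 4.6.1 Endpoint definition | Included |
| 4.6.2 Secondary outcomes | Outside two of nine as worded; inside seven |
| 5.2.1, if Intervention | Randomised in error (minor deviation) |
| 5.2.1, if Control | Not listed as a deviation |
| 7.1 Primary analysis | Included, as allocated |
| 8.1 CONSORT flow | Counted as an error in the Intervention Group only |

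**3. Is 5.2.1 likely to be out of date?** It uses under 35 years as the age error, while section 4.4.1 admits workers from 30. The two therefore conflict on age as well as department. The document history says that version 2.0 changed the inclusion and exclusion criteria. This suggests that 5.2.1 was not updated, although the history does not say which criteria changed.

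**4. Size.** Let p be the share of enrolled workers who are in production but not sewing. The SAP does not give p. With 630 per arm, rule 5.2.1 is expected to flag p × 630 Intervention workers and no Control workers on the department clause:

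| Assumed p | Flagged, Intervention | Flagged, Control |
|---|---|---|
| 0% | 0 | 0 |
| 10% | 63 | 0 |
| 20% | 126 | 0 |
| 30% | 189 | 0 |

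These rows show only how the rule behaves. They do not estimate p.

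**The case against.** The strongest objection is that the two terms may mean the same people. Section 10.2 draws its sampling frame from all trial subjects who leave, and then discusses the attrition of sew-ers when judging whether that frame is large enough. The authors may therefore regard all participants as sew-ers. If so, no worker is misclassified on department and the repair is purely verbal. This stands, and it is why no size can be claimed. The age conflict and the one-arm wording in 5.2.1 remain either way.

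Four stronger readings are tempting, but the SAP does not support them.

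- *A reader might infer that the secondary outcomes cover sewing only.* Seven of the nine name no department.
- *A reader might infer that non-sewing workers are left out of the trial's question.* The trial title in section 2, the rationale in 4.1 and the hypothesis paragraph in 4.2 speak of textile workers generally, and the endpoint covers each participant.
- *A reader might infer that these workers could drop out of the analysis and bias the hazard ratio or reduce power.* Section 7.1 keeps everyone as allocated, and section 5.2 classes the deviation as minor. Section 7.2 removes from the descriptive population only those randomised in error without consent. Section 9.6 uses exclusion restrictively, after a blinded review documented before lock. Exclusion on department is not planned.
- *A reader might infer that the department item in 4.4.1 is the newer text and must prevail.* The document history says only that the criteria changed, not that this item did.

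**Conclusion.** The inconsistency is real, with limited consequences. Section 4.4.1 on one side, and the objective in 4.6.1, two outcomes in 4.6.2, rule 5.2.1 and section 10 on the other, use different department terms that the SAP does not reconcile. Under intention to treat, the primary hazard ratio is the same whichever term is meant. Two things are affected: the population that the estimate is said to describe, and the randomised-in-error count, which differs by arm by construction if any non-sewing workers were enrolled.

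The number of such workers cannot be computed from the SAP and may be zero. The department part of this conclusion matters in practice only if production is broader than sewing. The conflict between 4.4.1 and 5.2.1 on age does not rest on that assumption.

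**What to change.** Before database lock:

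1. State one department definition and use it in 4.4.1, 4.6.1, 4.6.2, 5.2.1 and section 10. The trial team should confirm which workforce was actually enrolled. If the two terms are synonyms, one sentence saying so is enough.
2. Rewrite 5.2.1 so that randomised in error means failing any current section 4.4 criterion, in either arm. This settles age, department and the one-arm wording together.
3. State that workers randomised in error stay in the intention-to-treat analysis.
4. If production is broader than sewing, add department at randomisation to the 8.2 baseline table. A sewing versus other production subgroup is optional; section 9.2 already acknowledges limited power for its subgroup tests.

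The cost is a few lines of SAP wording and, under item 4, one field that should be available from human-resources records. If production is confirmed as the population, the stated conclusion becomes broader than sewing workers.

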### 4.4.2 Exclusion criteria

Shahi employees will be ineligible to participate if:

- have ocular pathology in either eye detected during the eye examination, or history of such disease based on self-report
- have a low likelihood of completing follow-up in the study due to current plans to move out of the area or leave employment at Shahi during the follow-up period

## 4.5 Interventions

Eligible participants will be randomly assigned to Intervention or Control Groups (1:1). Intervention group participants will receive free reading glasses after undergoing a vision screening at the factories, which will mark the beginning of the assessment period. In addition to receiving free reading glasses, participants in the Intervention Group will be eligible for free replacement glasses in the event of loss or damage throughout the trial. Control group participants will receive free reading glasses at the end of the assessment period (18 months after the beginning of the assessment period). An interim analysis will be performed by the trial statistician. If the Trial Management Group (TSG) terminates the trial on the recommendation of the trial statistician, then Control Group participants will receive free reading glasses at trial closure. The trial will be investigator-masked, but not participant-masked, because the investigators do not feel provision of zero-power glasses to the control group is ethical. However, participants will have limited knowledge of the study hypothesis, limiting potential placebo effects.

## 4.6 Definition of primary and secondary outcomes

### 4.6.1 Primary outcome

The primary objective of the study is to estimate the effect of the provision of free reading glasses on the retention of textile workers employed in Shahi's sewing department. The time-to-event endpoint for PROSPER III is defined as the time between randomization to

Intervention or Control Group and loss of employment at Shahi. Employment status for each participant will be assessed from trial entry to closure as recorded in Shahi's Human Resource Management Database.

#### 4.6.2 Secondary outcomes

The secondary outcomes are:

- reasons given by supervisor and colleagues of former sew-ers (separately) for workers no longer being employed at Shahi
- proportions of sew-ers who state they are satisfied or very satisfied with work, feel valued or very valued at work, and are likely or very likely to stay with current employer
- change in self-assessed productivity
- self-report of having been approached by their assigned Captain and/or a supervisor
- change in attitude towards eye health, glasses wear and uptake of eyecare services
- changes in skill grade and associated change in wage
- adherence with spectacle wear
- Quality of Life using the THRIVE Near Vision Quality of Life tool.
- intervention cost-effectiveness

#### 4.7 Hypothesis framework

PROSPER III is a superiority trial comparing glasses wear to non-wear. Analysis of the trial will entail calculation of treatment effect measures and confidence intervals to assess the difference between the two arms.

#### 4.8 Sample size & power

Previous retention trials in this setting have showed 18-20% of overall likelihood of attrition at 5 months follow-up, 50% overall likelihood of attrition at 12 months, 60% at 18 months, 70% at 24 months. Assuming a work retention rate of 50% at 1 year and 40% at 18 months in the Control group, we anticipate that our glasses intervention will increase retention by 20% in the Intervention group at 1 year (hazard of 0.8). Data analysis using a Cox proportional hazard model with 2-sided significance at the 5% level and 80% power yields a total sample size of 1,260 (630 in each group). No correction for attrition is required as attrition is the outcome and therefore no attrition from the sample is possible.

#### 4.9 Intervention allocation

Consenting participants eligible for the trial will be divided into four strata according to age (<median,  $\geq$ median), work tenure at the textile factory (<median,  $\geq$ median). Participants in each stratum will be randomized 1:1 with block size of four to either the Intervention or Control Groups. The randomisation sequence will be generated by the researchers at Good Business Lab and concealed until a worker is determined eligible and has agreed to participate. The field team will have a list provided by the textile factories of potential participants, their current age, tenure and baseline productivity. Study personnel will access the random assignment for each participant according to the correct age-tenure stratum only at the time of enrolment.

## 4.10 Data collection schedule

### 4.10.1 Data collection before trial

Demographic data will be collected through Shahi's Human Resource database and clinical information will be collected using VisionSpring's Eye Examination Form (Annexe 1).

### 4.10.2 Data collection during trial

Wage and employment status data will be collected on a daily basis from Shahi's Human Resource division. Employment status data will be assessed on a weekly basis over the 18-month intervention period. Intervention costs will be collected by VisionSpring and assessed at the end of the trial intervention period. Secondary outcome data will be collected using the following data collection forms

- Baseline Assessment (following eye examination)
- Endline Assessment (at the end of the 18-month intervention period)
- Spectacle Wear Compliance (on a weekly basis over the 18-month intervention period)
- Self-assessment of productivity by workers enrolled in the trial (once at the start and at the end of the study)
- Supervisor assessment of worker productivity for workers enrolled in the trial (once at the start and at the end of the study)
- Identification of trial participants leaving the employ of Shahi will occur every two months and telephone interviews will be scheduled in two phases (7 months and 16 months after the start of assessment period)

## 4.11 Interim analyses and stopping rules

An interim analysis on the primary outcome will be performed by the trial statistician. In the light of interim data on the trial's outcomes, adverse event data, accumulating evidence from other trials and any other relevant evidence, the statistician will inform trial management if in their view there is proof beyond reasonable doubt that the data indicate that any part of the protocol under investigation is either clearly indicated or contra-indicated, either for all participants, or for a particular subgroup of trial participants. Unless modification or cessation of the trial is recommended by the trial statistician, the investigators, collaborators, and administrative staff will remain ignorant of the results of the interim analysis. The accumulating trial data by arm and interim analyses will be confidential and will only be viewed by the principal investigator upon the recommendation of the trial statistician. The TMG will not be routinely privy to these interim reports. The trial statistician will make recommendations to the TMG based on the interim data.

## 4.12 Trial reporting

The trial will be reported according to the principles of the CONSORT statement.

## 5. PROTOCOL DEVIATIONS

A protocol deviation is defined as a failure to adhere to the protocol such as the wrong intervention being administered, incorrect data being collected and documented, errors in applying inclusion/exclusion criteria or missed follow-up visits due to error.

## 5.1 Major

The following will be defined as major protocol deviations:

- Enrolled workers have not provided Informed Consent
- Data considered fraudulent

## 5.2 Minor

The following will be defined as minor protocol deviations:

### 5.2.1 Participants randomised in error

- Employees < 35 years, or employed < 6 weeks, or not employed in the sewing department assigned to Intervention Group

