## 9.2 Pre-specified subgroup analysis

The consistency of the effect of the intervention across specific subgroups will be assessed using the statistical test of interaction. Note that this study was not designed to have sufficient power to test for interaction terms in these subgroup analyses; we will interpret the results with caution. Pre-specified subgroup analyses include:

- Sex
- Skill grade (<median,  $\geq$ median)
- Degree of Presbyopia (early presbyopia, reading glass powers < 1.25D; moderate presbyopia, 1.25D  $\leq$  reading glasses powers < 2.00D, advanced presbyopia: reading glasses powers  $\geq$ 2.00D)
- Age group (35 to 39 years, 40 to 49 years, 50 years and older)
- Compliance rate observed in the factory (<median,  $\geq$ median)
- Presenting binocular near visual acuity of N8 and worse

Subgroup analysis will be performed on the primary outcome and mean efficiency outcomes.

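### Workers aged 30 to 34 are eligible, yet SAP 5.2.1 counts employees under 35 as randomised in error and the 9.2 age subgroups start at 35

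*SAP*

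**What the plan says.** Two places set the lower age limit for entry at 30. The inclusion criteria (SAP 4.4.1) require that "they are aged 30 years or older". The objectives (4.2) describe the subjects as "textile workers aged 30 years and above with uncorrected presbyopia". The rationale in 4.2 fits that limit, since it says that loss of accommodation "due to presbyopia can begin as early as age 30 years". The exclusion criteria in 4.4.2 contain no age item.

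Two other places use 35. Section 5.2.1, under the minor deviations of 5.2 ("The following will be defined as minor protocol deviations"), lists as randomised in error: "Employees < 35 years, or employed < 6 weeks, or not employed in the sewing department assigned to Intervention Group". Section 9.2 pre-specifies the subgroup "Age group (35 to 39 years, 40 to 49 years, 50 years and older" and states: "Subgroup analysis will be performed on the primary outcome and mean efficiency outcomes".

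Nothing in the SAP explains or reconciles the two limits.

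**The concern.** A worker aged 32 who meets the other criteria is properly enrolled under 4.4.1 and is a participant randomised in error under 5.2.1. Section 5 defines a deviation as a failure to adhere to the protocol and includes mistakes in applying the eligibility criteria. Enrolling this worker is no such mistake, so the 5.2.1 rule also conflicts with the definition it sits under.

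Two outputs are at stake. The first is the deviation report and the CONSORT flow: 8.1 commits to reporting the number randomised in error, so eligible workers would be published as enrolment errors. The second is the age subgroup analysis. Workers aged 30 to 34 fall in no band, so the analyst must either drop them or create a band that was not pre-specified. Age matters here, because 4.2 reports a significant age-by-group interaction in the earlier tea-worker trial, with larger gains in older intervention participants. The workers without a category are those at the young end of that gradient.

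A further ambiguity lies in the closing words of the 5.2.1 bullet, which refer to assignment to the Intervention Group. If they qualify only the department item, the age rule covers both arms. If they qualify the whole bullet, it covers the Intervention arm alone, and the age count is one-sided by construction.

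**Working it through.** The plan states no figure on this point, so the check compares the limits and then sizes the overlap.

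**Step 1. Limits side by side**

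| SAP section | Rule | Ages 30 to 34 |
|---|---|---|
| 4.2 Objectives | 30 and above | In the study population |
| 4.4.1 Inclusion | 30 or older | Eligible |
| 4.4.2 Exclusion | No age item | Not excluded |
| 5.2.1 Randomised in error | Under 35 | Minor deviation |
| 9.2 Age subgroups | 35–39, 40–49, 50 and older | No band |

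The eligible ages that no 9.2 band covers are 30, 31, 32, 33 and 34. The eligible ages that meet the 5.2.1 rule are the same five.

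**Step 2. Number of workers affected**

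Inputs: 1,260 participants in total and 630 per group (4.8). The share aged 30 to 34, written s, is not given. The range used is an assumption: s from 5% to 20%, equal in both arms.

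- No band in 9.2: 1,260 × s. At 5%, 1,260 × 0.05 = 63; at 20%, 1,260 × 0.20 = 252.
- Counted as randomised in error, if the rule covers both arms: the same 63 to 252.
- Counted as randomised in error, if it covers the Intervention arm only: 630 × s. At 5%, 630 × 0.05 = 31.5, about 32; at 20%, 630 × 0.20 = 126. The Control count is 0 by definition.

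The counts are proportional to s. Each percentage point adds 1,260 × 0.01 = 12.6 workers in total, and a share near zero would give a count near zero.

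**Step 3. Where the effect stops**

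- 7.1 analyses all participants as randomised, so workers aged 30 to 34 stay in the primary comparison.
- 7.2 removes randomised-in-error cases from the baseline tables only where consent is missing.
- 9.3 enters age as a continuous variable, so its models need no age bands.

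What remains is the deviation and CONSORT count, and the age interaction test for the primary and mean efficiency outcomes.

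**The case against.** The best case against giving this much weight has four parts.

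*The size is unknown and may be small.* Entry requires reduced unaided near acuity in both eyes, and 4.2 says presbyopia usually becomes apparent functionally by about 40, so few participants may be under 35. This stands as a caution: the 5% floor is as much an assumption as the 20% ceiling. The contradiction itself does not depend on the share.

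*The consequences are limited.* The deviation is classed as minor, the primary analysis is by intention to treat, and 9.2 itself warns that the interaction tests are underpowered and will be read with caution. All of this is correct, and it keeps the point well below a threat to the main result. It does not make the published count right or supply the missing age category.

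*Section 9.2 does not say that workers outside the bands are dropped.* This is also correct. The plan leaves them undefined, and the alternative to dropping them is a band chosen at the analysis stage, which loses the benefit of pre-specification.

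*The intended limit is not certain.* The document history records that version 2.0 changed both the eligibility criteria and the subgroup analysis, and the bands in that version still start at 35. A limit left over from earlier text is a plausible explanation but only an inference. The operative inclusion criterion, the population statement and the rationale all point to 30, so the deviation rule and the bands should follow them unless the sponsor shows otherwise.

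**Conclusion.** The concern holds. The SAP's current text makes workers aged 30 to 34 eligible, labels them as randomised in error, and gives them no age subgroup. Under the assumed share of 5% to 20%, equal by arm, 63 to 252 of 1,260 workers have no band in 9.2. The false error count is 63 to 252 if 5.2.1 covers both arms, or about 32 to 126 of 630 against 0 in Control if it covers the Intervention arm only. The true share cannot be derived from the document. The effect is confined to deviation and CONSORT reporting and to one pre-specified subgroup analysis; the primary estimate is unaffected. The text should be corrected, but the main conclusion of the trial does not depend on it.

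**What to change.** 1. In 5.2.1, change the age limit to under 30 to match 4.4.1, and split or reword the bullet so that each item applies to participants in either arm, in line with the arm-neutral definition in section 5.
2. In 9.2, extend the youngest age band to include ages 30 to 34, for example 30 to 39 years, so that every eligible participant has a category.
3. If the sponsor in fact intended 35, then 4.2 and 4.4.1 are the sections in error. Either way, 4.2, 4.4.1, 5.2.1 and 9.2 must state one limit.

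The same 5.2.1 bullet refers to the sewing department where 4.4.1 refers to the production department. That is a separate mismatch, but it can be settled in the same edit.

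The cost is SAP wording only. The changes should be made and dated before outcome data are analysed, so that the youngest age band is not chosen with results in view.
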